4.3 Handling of Dropouts or Missing Data

Subject-level listings will present data as reported. Missing or partially missing dates that are required for date-dependent definitions (e.g., treatment-emergent adverse events (TEAEs), concomitant medications) will be assumed to be the most conservative date possible.

For the primary efficacy endpoint, no imputation will be performed and the mixed-model repeated measures (MMRM) analysis will use all available data to estimate the mean treatment effect.

An AE with a completely missing start date will be considered treatment-emergent; similarly, an AE that started the same month and year as IP administration but with missing start day will be considered treatment-emergent.

AEs with missing seriousness will be counted as “serious” in tables and missing in listings; likewise, AEs with missing severity will be counted as “severe” in tables and missing in listings, and AEs with missing relatedness to the IP and/or IP administration procedure will be counted as “possible” and missing in listings.

Medical history with missing stop dates will be considered ongoing. Medications with missing stop dates will be considered in concurrent use during the study and counted in the summary table of concomitant medications unless the start date is after the last IP administration.

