6.1 Primary Efficacy Endpoint

The primary efficacy endpoint is change from baseline to Month 12 in the mid-level (elbow) dimension of the PUL 1.2. The hypothesis set to be tested is:

$$H_0: \mu_c - \mu_p = 0$$

$$H_a: \mu_c - \mu_p \neq 0$$

where μ_c and μ_p are population mean absolute changes from baseline in CAP-1002- and placebo-treated patients, respectively.

A MMRM analysis will be used to analyze the primary efficacy endpoint using the ITT population. The results for Month 3, 6, 9 and 12 visits will be modeled with visit, treatment, and treatment-by-visit interaction as the main effects; baseline measurement, site and binary stratification of entry item score of the PUL 1.2 at screening (2, 3 vs. 4, 5) will be included as covariates in the model. An autoregressive (AR(1)) covariance structure will be the covariance structure to model within-subject errors. The Kenward-Roger's (K-R) approximation will be used to estimate the denominator degrees of freedom. The primary comparison will be the contrast between CAP-1002 and placebo at Month 12.

As a supportive analysis, the analysis may be evaluated in the PP population.

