2.3.3. Outlier Removal

In addition to conducting the non-parametric analyses, outlier (unusual) observations that are driving the non-normality can be removed so that the normality assumptions of the pre-specified parametric model hold. After removal of the outlier subject(s) from the data, the residuals can be reassessed for normality both graphically and inferentially via the Shapiro-Wilk Test.

Although outlier removal can be a useful sensitivity analysis, it is not usually an appropriate primary approach because it violates the intention-to-treat principle that is central to unbiased assessment and is a focus of ICH E9 statistical guidance. Removing just one subject in this small

sample would remove 5% of the data and is therefore deemed less useful than non-parametric analyses, especially given that no a priori cut off for identifying outliers was pre-specified.

2.3.4. *Imputation of Missing Data*

The selected endpoints to be evaluated using imputation of missing data are as follows:

- change from baseline for the mid-level (elbow) dimension of the PUL 1.2 at Months 3, 6, 9, and 12
- change from baseline for the combined high-level (shoulder), mid-level (elbow), and distal-level (hand and wrist) dimensions of the PUL 2.0 at Months 3, 6, 9, and 12
- change from baseline for LVEF as assessed by cardiac MRI at Months 3, 6, 9, and 12

The sensitivity of the analysis of the selected endpoints above to missing data will be evaluated in the ITT population using two different techniques to impute that missing data:

1. Last z-score carried forward
and
2. Multiple imputation with 500 replicates using control-based pattern imputation for monotone missing data

To implement the first method, z-scores will be calculated by visit using all raw observed values at that visit prior to carrying the last available z-score forward to any missing data points. Once all missing data is imputed with the last available z-score, change from baseline in raw z-score will be calculated and analyzed using the primary MMRM, and percentile ranked change from baseline in raw z-score will be calculated and analyzed using the primary MMRM.

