Subjects who do not have data for an intermediate visit but do have data for subsequent visits may reasonably follow the same trajectory as subjects in their respective arm, but subjects who discontinue treatment may follow the same trajectory as placebo-arm subjects. To use this reasoning with multiple imputation, intermediate missing data will first be imputed with random sampling using non-missing data from that subject's respective treatment arm so the resulting missing data pattern will be monotone. The remaining missing data will then be imputed with random sampling from non-missing placebo arm data. Once all missing data is imputed, change from baseline will be calculated and analyzed using the primary MMRM, and percentile ranked change from baseline will be calculated and analyzed using the primary MMRM.

2.3.5. *Additional Transformations*

The sensitivity of the analysis of change from baseline for the mid-level (elbow) dimension of the PUL 1.2 at Months 3, 6, 9, and 12 to data transformations will be evaluated in the ITT population using two additional data transformation methods on the raw baseline and change from baseline values:

1. Ordinal ranking
and
2. Cube-root transformation

Once the data is transformed using the above methods, the transformed values will be analyzed using the primary MMRM.

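### SAP Addendum 2.3.4 states no conditioning on the subject's own baseline or earlier visits, so as written an imputed change mixes two subjects and the missing-data check loses sensitivity

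*SAP*

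**What the plan says.** The main analysis leaves missing values alone. SAP 4.3 states: "For the primary efficacy endpoint, no imputation will be performed". The post-hoc Addendum, section 2.3.4, then adds two imputation techniques as sensitivity analyses for mid-level PUL 1.2, total PUL 2.0 and LVEF. The second is named as follows: "Multiple imputation with 500 replicates using control-based pattern imputation for monotone missing data".

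The operating steps for that technique are:

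- Gaps followed by later data: "intermediate missing data will first be imputed with random sampling using non-missing data", with the donors coming from the subject's own arm.
- All other gaps: "The remaining missing data will then be imputed with random sampling from non-missing placebo arm data".
- Afterwards: "Once all missing data is imputed, change from baseline will be calculated and analyzed using the primary MMRM". A percentile-ranked version of the change is analysed as well.

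The stated reason for using placebo data is that "subjects who discontinue treatment may follow the same trajectory as placebo-arm subjects". The analysis model in SAP 6.1 adjusts for "baseline measurement, site and binary stratification of entry item score of the PUL 1.2 at screening".

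None of the three steps mentions the subject's own baseline, earlier visits, site or stratum.

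**The concern.** Change does not exist until the last step, so what is sampled is a visit value. If that value is a plain random draw, the imputed change is the donor's score minus this subject's baseline. A trajectory is a course from one's own starting point, and such a draw replaces the starting level as well. Gaps at successive visits may also come from unrelated donors, so the filled values lose the serial correlation that the AR(1) model assumes.

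At stake is how informative the check is. Protocol 14.6.2 foresaw multiple imputation for the primary endpoint where needed to keep subjects in the analysis, and SAP 4.3 drops it. Addendum 2.3.4 is therefore the only missing-data sensitivity analysis described for the Month 12 PUL result. With 20 subjects, one or two imputed values can move that check noticeably.

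**Working it through.** The plan gives no figure for this imputation, so there is nothing to reproduce. Total sample size (20), 1:1 allocation, two-sided 0.05 and baseline as a covariate come from the documents. The even split of 10 per arm, the SDs, the correlations and the numbers missing are assumptions.

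**Step 1: one subject.** Let the placebo mean baseline be m and the placebo mean change be d. A subject with baseline m + 6 receives a donor score that averages m + d, so his imputed change averages (m + d) − (m + 6) = d − 6. With equal SDs at both visits and baseline-to-visit correlation ρ, conditioning on his own baseline gives d + (ρ − 1) × 6. At ρ = 0.9 that is d − 0.6.

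**Step 2: spread of the imputed change.** With SD s at each visit, an observed change has SD s√(2(1 − ρ)). An unconditional draw minus own baseline has SD s√2. The ratio is 1/√(1 − ρ): 1.83 at ρ = 0.7, 2.24 at 0.8, 3.16 at 0.9 and 4.47 at 0.95.

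**Step 3: does the baseline covariate repair it?** Among observed subjects, change regresses on baseline with slope ρ − 1. Among unconditional draws the slope is −1. The model fits one common slope. Around the slope ρ − 1, residual variance is s²(1 − ρ²) for an observed subject and s²(1 + ρ²) for an unconditional draw. The SD ratio at ρ = 0.9 is √(1.81/0.19) = 3.09, so the covariate removes little of the excess.

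**Step 4: effect on the treatment contrast.** All runs below use Rubin's rules.

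*Month 12 ANCOVA with baseline, in SD units* (10 per arm, true effect 0.3 SD, placebo decline 0.3 SD, 400 trials, 100 imputations). Mean SE, unconditional draw v placebo regression on own baseline:

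| ρ | 1 CAP-1002 missing | 2 CAP-1002 + 1 placebo | 3 CAP-1002 + 1 placebo |
|---|---|---|---|
| 0.7 | 0.355 v 0.345 (+3%) | 0.401 v 0.375 (+7%) | 0.421 v 0.399 (+6%) |
| 0.9 | 0.257 v 0.212 (+21%) | 0.340 v 0.232 (+47%) | 0.370 v 0.249 (+49%) |
| 0.95 | 0.219 v 0.153 (+43%) | 0.311 v 0.168 (+85%) | 0.343 v 0.179 (+92%) |

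Mean estimates barely differ. At ρ = 0.9 with 3 + 1 missing both are 0.210, but the trial-to-trial SD of the estimate is 0.220 v 0.158.

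*Month 12 ANCOVA in PUL points* (SD of change 2.5, one or two CAP-1002 dropouts). The SE inflation against baseline-conditional placebo imputation is 3-4% at ρ = 0.7, 8-14% at 0.8, 24-40% at 0.91 and 46-70% at 0.95. With equal SDs, ρ = 1 − 2.5²/(2s²), so baseline SDs of 4, 6 and 8 points correspond to ρ of 0.80, 0.91 and 0.95.

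*Full SAP 6.1 model* (site, stratum, AR(1) with parameter 0.7; baseline SD 4 to 8; assumed sites of 1, 1, 2, 2, 2, 4, 4, 4; Months 9 and 12 missing; 40 imputations, 150 trials). The comparator here is drawing a placebo donor's change. The SE is 1.43 to 1.72 against 1.26 to 1.30 with one dropout (about 13% to 32% larger), and 1.55 to 2.08 against 1.31 to 1.33 with two (about 18% to 56%).

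**Step 5: error rates.** Month 12 ANCOVA, baseline SD 4 or 8, one or two CAP-1002 dropouts, 60 imputations, 1,000 trials per setting, against placebo change donors. With no true effect, rejection at 0.05 is 0.2% to 1.2% against 1.1% to 3.6%. With a true effect of 2 points, two dropouts and baseline SD 4, power is 6.5% against 14.1%.

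**The case against.** The strongest reply is that the text may be loosely worded and the method sound. Control-based pattern imputation for monotone data ordinarily suggests a sequential model. Filling intermediate gaps first so that the pattern becomes monotone is needed by such a model and not by unconditional draws. The word raw appears only in the description of the other technique, the carried-forward z-score. A reader might infer that the Addendum definitely uses unconditional donors; the documents do not settle that. What stands is that the steps as written contain no conditioning and someone programming from them could omit it, so the text needs correcting under either reading.

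Second, calculating change after imputation is not a fault in itself. It is harmless once the imputation uses the subject's own baseline and earlier visits. For mid-level PUL 1.2 the baseline is available, because SAP 4.5 reports that mITT, which requires one, equals ITT. This reply stands.

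Third, a reader might infer that the method could manufacture a positive result or that baseline differences swamp the check. The runs show the opposite of the former: rejection under the null falls. The latter needs a high correlation that the documents do not give; at 0.7 the inflation is only 3-7%.

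Fourth, the ranked analysis limits how extreme one imputed change can be. The figures above cover only the unranked version.

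Finally, this is one of two post-hoc techniques, and SAP 4.4 treats p-values after the interim analysis as nominal. That limits the consequence but does not make the described steps match their stated rationale.

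**Conclusion.** The point holds as a defect in how one sensitivity analysis is described. Followed as written, the imputed changes do not follow a placebo course from the subject's own starting level, and baseline adjustment does not restore it. The harm is noise and lost sensitivity. There is no shift in the average estimate relative to conditional placebo imputation and no excess of false positives. In a single trial the estimate still moves with the baseline level of whoever dropped out.

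The size depends on the correlation: about 3-4% on the SE at 0.7, 8-14% at 0.8 and 24-70% at 0.91 to 0.95, for one or two CAP-1002 dropouts with 10 per arm. It is nil if nothing is missing. These figures assume equal visit SDs, and the ANCOVA runs leave out site and AR(1) terms and choose dropouts without regard to baseline. A wide baseline spread is plausible, since eligibility admits PUL entry scores 2 to 5 and both ambulatory and non-ambulatory subjects, but the documents give no SD, correlation or count of missing values.

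Nothing here reaches the primary MMRM. A reader should not take this as a reason to doubt the Month 12 result itself.

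**What to change.** In Addendum 2.3.4, replace the random-sampling wording with sequential (monotone) regression imputation that conditions on the subject's own baseline and earlier visits. Fit it in the subject's own arm for intermediate gaps and in the placebo arm for gaps after discontinuation. Alternatively, draw one placebo donor's whole remaining run of changes and add it to the subject's own baseline, which keeps successive visits correlated. Report the number of imputed values by arm and visit. Calculating change after imputation can then stay as it is.

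The cost is a few sentences and a rerun of one sensitivity analysis, with no new data. A small downside is that a regression fitted to about 10 placebo subjects is itself imprecise.

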Results from a non-parametric and / or data-transformed analyses can be compared to the corresponding results from a parametric analysis to assess the consequences of departures from assumed conditions. Additional sensitivity analyses can be used to assess the robustness of other aspects of the primary and sensitivity modeling approaches².

2.1. Assessment of Departures from Normality Assumptions and their Consequences in the HOPE-2 Trial

The residuals from the pre-specified model of the primary analysis in the HOPE-2 trial will be plotted in a histogram and inspected visually. An inferential assessment for departure from normality will be implemented via the Shapiro-Wilk test.

A data transformation approach will be implemented that retains as many aspects of the primary analysis as possible. This approach will model changes from baseline (and baseline values) after transforming (converting) them to percentile ranks. The primary model will then be fit to the percentile ranks. The estimates from this alternative analysis will be re-transformed back to the original scale to facilitate interpretation on the original scale.

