2.2. Details of the Data Transformed Model

The primary efficacy analysis is change from baseline to Month 12 in the mid-level (elbow) dimension of the PUL 1.2 assessed via a parametric linear MMRM model to compare treatment groups in mean change from baseline to Month 12. If non-normality of the residuals is identified via the procedure identified in Section 2, a data transformation will be applied and then the primary MMRM model will be applied to the transformed data. This primary MMRM model on the transformed data tests the same hypotheses.

$$\begin{aligned} H_0: \mu_C - \mu_P &= 0 \\ H_a: \mu_C - \mu_P &\neq 0 \end{aligned}$$

where μ_C and μ_P are population mean of changes from baseline in CAP-1002- and placebo-treated subjects, respectively, which on the transformed data is also a test of the medians because the mean and the median of a distribution of percentiles are the same.

To implement this model, an MMRM analysis will be used to analyze the percentile ranked primary efficacy endpoint data using the same pre-specified ITT population. Data from the post-baseline visits (Month 3, 6, 9 and 12) will be modelled with visit, treatment, and treatment-by-visit interaction as the main effects, and ranked baseline score, site and binary stratification of entry item score of the PUL 1.2 at screening (2, 3 vs. 4, 5) as covariates. A First Order Autoregressive (AR(1)) covariance structure will be used to model the within-subject errors. The Kenward-Roger's (K-R) approximation will be used to estimate the denominator degrees of freedom. The primary comparison will be the contrast between CAP-1002 and placebo at Month 12.

For a given outcome, this analysis will be implemented by calculating the percentile rank of each change-from-baseline value relative to all observed change-from-baseline values for that outcome (across all subjects and all post-baseline observation times). The percentile ranked change-from-baseline is the dependent variable in the model.

This modeling approach will be applied to primary, secondary, and some exploratory endpoints for the ITT Population only.

In addition, for PUL and Cardiac MRI outcomes, Global Statistical Tests³ (GST) will be calculated as the averaged percentile ranked change-from-baseline.

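### The ordinal-ranking check in SAP Addendum 2.3.5 is, on its natural reading, the percentile-rank model of 2.2 in other units, so its agreement would say nothing about robustness to the transformation

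*SAP*

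**What the plan says.** The percentile-rank model is set out in SAP Addendum 2.1 and 2.2. Section 2.1 gives the variables: "This approach will model changes from baseline (and baseline values) after transforming (converting) them to percentile ranks". Section 2.2 gives the ranking as "calculating the percentile rank of each change-from-baseline value relative to all observed change-from-baseline values for that outcome", in one pool taken "across all subjects and all post-baseline observation times". It continues: "The percentile ranked change-from-baseline is the dependent variable in the model". The covariates are "ranked baseline score, site and binary stratification of entry item score", and the covariance is that of the primary MMRM: "A First Order Autoregressive (AR(1)) covariance structure will be used to model the within-subject errors". Degrees of freedom are Kenward-Roger.

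Section 2.3 introduces its sensitivity models as checks on the model just described. Within it, 2.3.5 examines sensitivity to the choice of transformation for mid-level PUL 1.2 in the ITT population, "using two additional data transformation methods on the raw baseline and change from baseline values". The first method is listed as "1. Ordinal ranking" and the second is a cube root. Both are fitted with the primary MMRM.

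For ordinal ranking the addendum gives no ranking pool, no tie rule and no statement of how it differs from the percentile rank. Section 2.2 gives no tie rule either.

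**The concern.** A sensitivity analysis is informative only if it could have disagreed with the result it tests. Item 1 takes the same two variables as 2.2, ranks them, and fits the same model. If the ranking is done in the same way, the only change is the unit of measurement.

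The addendum is openly post hoc and the trial has 20 subjects, so the weight given to the percentile-rank result depends on its supporting checks. Section 2.3.5 offers two checks on the transformation. If one is bound to agree, counting both overstates the support.

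**Working it through.** The documents give no figure on this point, so there is none to reproduce. The check is algebra, followed by a numerical confirmation.

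**Inputs.** 20 randomized subjects, 1:1 (SAP 3.1). Four post-baseline visits, fixed effects and AR(1) (SAP 6.1; Addendum 2.2). Same variables and same MMRM for item 1 (Addendum 2.3.5).

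**Step 1: relation between the ranks.** Let r be the rank of a change among the N pooled changes. Common definitions of the percentile rank are 100r/N and 100(r − 0.5)/N. With complete data N = 20 × 4 = 80, giving 1.25r and 1.25r − 0.625. For baseline, ranked over 20 subjects, they are 5r and 5r − 2.5. With one pool and one tie rule, each is a constant plus a constant times r, with the same constants for every observation.

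**Step 2: effect on the model.** Replace the outcome y by a + cy with c > 0. The intercept absorbs a, and every other coefficient and its standard error is multiplied by c. The REML likelihood shifts by a constant, so the estimated AR(1) correlation does not move. A linear change of the baseline covariate alters only its own coefficient and the intercept. For the Month 12 contrast:

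t = (c × estimate) / (c × SE) = estimate / SE.

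The Kenward-Roger degrees of freedom are scale-free, so p is unchanged too. This holds whatever the data.

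**Step 3: numerical check.** 40 trials were simulated with 20 subjects, four visits, some missing visits, and whole-number changes. Sites followed Addendum 2.3.2: two with one subject and three with one per arm, with the other 12 subjects assumed to lie in two sites of six. The model was a REML AR(1) fit with the addendum's fixed effects. Degrees of freedom were fixed at 12 throughout, because Kenward-Roger was not coded. In the eight trials inspected individually there were 74 to 77 changes on 10 to 13 distinct values. The data model is assumed, so apart from the first row the p-values are illustrative.

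Month 12 p-value compared with the pooled, mid-rank percentile model:

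| Version | Absolute difference in p | Trials crossing 0.05 |
|---|---|---|
| Ordinal, same pool, mid-ranks | maximum 2e-08 | 0 of 40 |
| Ordinal, pooled, low ties | median 0.011 | 0 of 40 |
| Ordinal, pooled, high ties | median 0.005 | 2 of 40 |
| Ordinal, pooled, dense ties | median 0.019 | 3 of 40 |
| Ordinal, within visit, mid-ranks | median 0.028 | 4 of 40 |
| Cube root | median 0.048 | 3 of 40 |

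With ties broken by record order, each trial was refitted under 40 random orders. The range of p within a trial had median 0.115 and maximum 0.59, and it straddled 0.05 in 9 of 40 trials.

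**One simulated trial** (74 changes, 11 distinct values): percentile rank p = 0.0406; ordinal with mid-ranks 0.0406; ties broken at random 0.018 to 0.093; within visit 0.038; dense 0.023; cube root 0.116.

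**The case against.** The strongest reply is that the identity is conditional. Section 2.2 states its pool, but 2.3.5 states neither pool nor tie rule. Within-visit ranks, or low, high or dense ties set against mid-rank percentiles, give p-values that are reproducible and different, as the table shows. This stands. A reader might infer that item 1 must agree with 2.2 in every case, or that the only alternative is an order-dependent result. The documents support neither. What remains is that the reading needing no unstated choice is the redundant one. Where only the low or high tie rule differed, any disagreement would reflect the handling of ties.

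A reader might also infer that ties would be broken by arm, because SAP 4 sorts by treatment first. That rule governs listings, not analysis datasets, and nothing says ties are broken by record order.

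The PUL description in Protocol 11.3 gives no item scoring, so tied whole-number scores are an assumption. The tie-related results depend on it; the identity does not.

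Finally, the reach is limited. Item 1 concerns one endpoint in one population, the addendum calls itself post hoc, and SAP 4.4 treats p-values after the interim analysis as nominal. The cube root, the permutation test, the site models, outlier removal and the imputation analyses remain. It would be wrong to conclude that all of 2.3.5, or the pre-specified MMRM, is undermined. The text also does not say how agreement would be reported.

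**Conclusion.** The point holds conditionally. With the pool of 2.2 and a common tie rule for both rankings, item 1 of 2.3.5 and the percentile-rank model are one analysis with one p-value, and item 1 cannot serve the purpose that 2.3 and 2.3.5 give it. That rests on algebra alone. Under any other reading item 1 is undefined as written: its p-value depends on a pool or tie rule that the addendum does not state, and would be arbitrary if ties were broken by record order. How much those choices would matter in this trial cannot be known from the documents. The correction is worth making because it changes what the robustness section can conclude.

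**What to change.** Replace item 1 of Addendum 2.3.5 with a transformation that is not a linear function of the percentile rank, for example normal scores or ranks formed within visit, using mid-ranks for ties. Otherwise delete it. State the tie rule in 2.2, and the pool and tie rule for any rank-based replacement. If ordinal ranking has already been run, report it and the percentile-rank model as one analysis and count them once. Cost: one line of wording and one model run, with no new data.
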